The SAGES I cohort will be followed with neuropsychological testing to achieve a minimum of 8 years of follow-up under a standing IRB protocol (SAGES I Protocol: 2009P-000262). From the SAGES I cohort, we will invite a subgroup (N=148) of participants who previously agreed to be contacted for other studies to undergo phlebotomy, lumbar puncture (LP), non-invasive transcranial magnetic stimulation (EEG/TMS) and magnetic resonance imaging (MRI) procedures. The SAGES I Subgroup will be called SAGES Select. SAGES Select participants who are not eligible to undergo LP to obtain CSF, will be invited instead to undergo an amyloid-PET scan. We will also continue long-term follow-up for the entire sample (N=560) over 8-12 years of follow-up under IRB protocol 2009P-000262.

SAGES II (n=460) will be newly enrolled and followed at 1, 2, 6, 12, 18, 24, and 36 months after enrollment with neuropsychological testing and will be invited to undergo the same procedures as SAGES I SELECT, with the exception that CSF will be collected prior to spinal anesthesia if possible (rather than a separate LP procedure). SAGES II participants for whom we could not get CSF at anesthesia induction will be invited to undergo an amyloid-PET scan after the one month follow-up visit. The 5 interlinked projects utilize these cohorts as described in Table 4 and below.

Table 4: Field Core Samples for the delirium P01 Renewal Project								
Cohorts	New for	Sample Size	Projects	Purpose				
	Renewal?							
	SA	GES I Cohorts						
Total SAGES I (dementia-free) sample	No	560	1, 4	Continued follow-up (2 waves, minimum				
				5 & 8 yrs post-op), prediction of LICD				
				(Protocol: 2009P-000262)				
SAGES I Select nested cohort (probability	Yes	148	ALL	CSF (or amyloid-PET) AD,				
sampling based on frequency matching)		(subset of 560)		Inflammatory, MRI, IMS/EEG				
				biomarkers of delirium (obtained ~4 yrs				
				after index admission) & LTCD (8 yrs				
				post-op)				
	SA	GES II Cohorts						
Total SAGES II Sample (MCI enriched-	Yes	460	1,2,4	Prediction of delirium and 18-36 mo				
15%)				CD—CSF AD(or amyloid-PET) &				
				inflammatory biomarkers				
SAGES II Neuroimaging and	Yes	180	3,4,5	MRI and TMS/EEG biomarkers of				
Neurophysiology Cohort (MCI enriched-		(subset of 460)		delirium, &18-36 mo CD				
25%)								
Table Abbreviations: LTCD-long term cognitive decline, 18-36 mo CD-18 to 36 month cognitive decline, MRI-magnetic resonance imaging,								

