TMS/EEG-transcranial magnetic stimulation-electroencephalography, MCI-mild cognitive impairment, CSF-cerebrospinal fluid, AD-								
Alzheimer's Disease								

A.2.1 Project 1

Project 1 will investigate the inter-relationship of delirium and long-term cognitive decline (LTCD) with molecular biomarkers of AD pathology according to 3 general components of the new "ATN" (Amyloid– β [A β], Tau, Neurodegeneration) descriptive classification scheme for AD biomarkers with the following specific aims: (1) to examine the relationship between baseline cerebrospinal fluid (CSF) AD biomarkers (CSF A β_{42} , total tau [t-tau], phospho-tau tau/A β_{42} ratios, and neurofilament light [NFL]), sampled prior to spinal anesthesia, and development of post-operative delirium and cognitive decline over 18-36 months in a new cohort of 460 older persons undergoing joint replacement surgery (SAGES II); (2) to evaluate associations of history of delirium and AD biomarkers (CSF biomarkers or amyloid PET imaging, sampled near 4 year follow-up) with LTCD (over a minimum of 8 years) in a probability sample from SAGES I (N=148, SAGES I SELECT): 74 patients who developed delirium during the initial hospitalization and 74 who did not develop delirium during the initial or subsequent hospitalizations; and (3) after correlating CSF (or amyloid PET imaging) and plasma levels of novel SiMoA assays of t-tau and NFL obtained at follow-up in the SAGES I SELECT probability sample (N=148), to examine the relationship of pre-operative levels of these markers obtained from stored plasma with delirium incidence/severity and LTCD following delirium.

This project will probe whether fluid biomarkers identify patients who are more vulnerable to delirium, and are most likely to have cognitive decline following delirium. By probing the relationship of delirium and AD biomarkers, we will be well positioned to advance our mechanistic understanding and to develop more effective intervention strategies to forestall LTCD associated with delirium and AD. Moreover, this study may lay the groundwork for identification of potential plasma biomarkers for AD and related dementias (ADRD). If our hypotheses are confirmed, this study will offer compelling support for the importance of prevention of delirium to forestall the progression of cognitive decline in AD/ADRD.

A.2.2 Project 2

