Aim 2: To use mass cytometry (CyTOF) to characterize circulating immune cells associated with delirium and LTCD, and then validate these findings in an independent sample. Sample Size Justification: We base the power analysis for this aim on the pilot study of 7 non-delirious patients with percent of cell types CD45+CD11c+CD14+monocytes to total number of cells, measured at PREOP and POD1. The median of the paired differences was 10.15 with range 10.07-15.19, and the mean was 10.62 with SD of 6.55. We plan to use 40 matched pairs. Since this observed mean paired difference is for the surgery effect and not the delirium effect, we use 50% of this difference as the clinically significant delirium effect. We also assume that the signal to noise ratio is similar for the delirium effect, thus SD is expected to be 6.55. With these assumptions, we obtain a power of 0.98 for H2A. For H2B, focused on LTCD, assuming a larger effect size of 60% of the observed surgical effect, we obtain a power estimate of 0.94. For H2C, the validation sample with 40 matched pairs from SAGES II, we consider a cell surface marker with a relative risk of 1.6 with delirium compared to no delirium. With type-I error at 0.05, we obtain a power estimate of 0.82.

Aim 3: To measure CRP and the Walston inflammatory index in banked plasma, and freshly collected plasma and CSF, from a probability sample of 148 SAGES I participants (SAGES I SELECT). Sample Size Justification: For Aim 3, we have 148 subjects, probability sampled for delirium (74 with and 74 without) and frequency matched for age and baseline GCP. The predictors are the measured levels of plasma inflammatory markers, and CSF inflammatory and AD biomarkers. The outcomes are delirium and LTCD. We use a relative risk of 1.5 as the threshold of clinical significance, and a type-I error of 0.05, and calculate 0.84 power for delirium and 0.80 for LTCD. Thus, we have very good power for this Aim.

Project 3

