positivity has the steepest slope) requires that in addition to biomarker positivity being related to slope, delirium must be related to slope (as shown previously)²² and that the two effects are at least partially independent (i.e., the effect of biomarker positivity is only partially mediated by delirium). Aim 2 Analyses: The goal of Aim 2 is to evaluate associations of delirium and CSF or PET AD biomarkers sampled near 4 year follow-up among delirium cases and controls (n=74 each group). Control variables will include age, gender, race, education, Charlson, depression, functional impairment, surgery type, IQCODE, and baseline GCP score. Missing data will be handled using multiple imputation (50 imputations) and the chained equations approach.⁷² Hypothesis 2a. This hypothesis will be evaluated using generalized linear mixed effect modeling as described above for H1b, applying an approach similar to what we have used in our prior publications.²² The outcome is the composite measure, GCP, 55,73 and the main exposures are delirium group, time, and their interaction. A faster rate of LTCD among those with delirium is demonstrated by a significant interaction term for delirium group by long-term time trend. Hypothesis 2b. This hypothesis will be tested with generalized linear effects models as in H2a with biomarker positivity as the primary exposure, rather than delirium. We assume higher rates of biomarker positivity than in Aim 1, since 50% will have delirium and the overall group will have higher rates of cognitive impairment by frequency matching.

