Aim 3 Analysis: For H3A, the analytic strategy will be similar to that described in Aim 1 with measured levels of inflammatory proteins (and the inflammatory index) being the independent variables, and delirium and LTCD being the outcomes. We will examine plasma markers at PREOP, POD2, and LTFU, and CSF at one time point, LTFU. We anticipate seeing the lowest levels of inflammatory markers in the group without delirium and slow rates of LTCD, and the highest levels in those with delirium and faster rates of LTCD. We will perform multivariable analyses using generalized linear models with a log link for delirium incidence, and identity link for continuous LTCD. In H3B, to examine interactions with CSF AD biomarkers, we will select the most predictive inflammatory (IL-6, CRP, sTNFR1, or the inflammatory index) and AD biomarker (A β_{42} , t-tau, p-tau, or p-tau/A β_{42} ratio) and put both into the generalized linear model together. We expect significant independent effects of both inflammatory markers and CSF AD biomarkers on delirium and LTCD.

Project 3

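### Project 2 Aim 3 models CSF and plasma taken about 4 years after surgery in SAGES I SELECT as predictors of the index delirium, although these samples follow the delirium and may reflect it

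*Protocol*

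**What the plan says.** Protocol B.2.3, Project 2, Aim 3 Analysis (H3A) has "measured levels of inflammatory proteins (and the inflammatory index) being the independent variables, and delirium and LTCD being the outcomes", fitted as "generalized linear models with a log link for delirium incidence, and identity link for continuous LTCD". On timing it states: "We will examine plasma markers at PREOP, POD2, and LTFU, and CSF at one time point, LTFU". H3B then puts the most predictive inflammatory marker and the most predictive AD marker into one model, and the section concludes: "We expect significant independent effects of both inflammatory markers and CSF AD biomarkers on delirium and LTCD".

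The power paragraph for the same aim (B.1.3) assigns the same roles: "The predictors are the measured levels of plasma inflammatory markers, and CSF inflammatory and AD biomarkers. The outcomes are delirium and LTCD".

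Table 4 (A.2) gives the date of SELECT sampling: "biomarkers of delirium (obtained ~4 yrs" after the index admission, with LTCD followed to 8 years post-op.

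Project 1 Aim 2 uses the same SELECT samples. A.2.1 relates the marker, alongside delirium history, to decline: "AD biomarkers (CSF biomarkers or amyloid PET imaging, sampled near 4 year follow-up) with LTCD (over a minimum of 8 years". For H2b, B.2.3 says: "This hypothesis will be tested with generalized linear effects models as in H2a with biomarker positivity as the primary exposure, rather than delirium".

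**The concern.** A model for incidence of an event, with markers as predictors and a stated expectation of effects on that event, makes a claim about direction. In SELECT, CSF exists only at LTFU, so the direction cannot be as claimed. The protocol itself supplies the opposite path. B1 calls it unclear whether delirium itself leads to lasting impairment, and B2 cites evidence that delirium can lead to neuronal death. A raised marker at year 4 in the delirium group is what that path would produce.

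At stake is the reading of Project 2 Aim 3. A trace of damage already done could be reported as a marker of vulnerability to delirium, and the joint model (H3B) could be read as showing independent causes. Frequency matching on baseline GCP and age does not remove marker change that occurs after the delirium.

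**Working it through.** **1. Order of events in SELECT**

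| Measurement | Time | Order relative to index delirium |
|---|---|---|
| Plasma PREOP | before surgery | precedes it |
| Plasma POD2 | hospital stay | concurrent |
| Plasma LTFU, CSF LTFU | about 4 years (Table 4, A.2.1) | follows it in every case |

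The fault is confined to the last row. Elsewhere the protocol orders events correctly. Project 1 Aim 3 uses stored pre-operative plasma for delirium. Project 5 Aim 3, in the same SELECT cohort, relates delirium history to later physiology, includes time since the index stay as a covariate, and treats subsequent decline separately. In SAGES II, CSF is drawn immediately before the operation (A.4.8).

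**2. The plan's own power figures for Project 2 Aim 3**

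B.1.3 gives 0.84 (delirium) and 0.80 (LTCD) for a relative risk of 1.5 and N = 148. Marker prevalence or SD and the LTCD cut-off are not given, so these cannot be reproduced. Plausible two-sided set-ups for delirium give 0.63 to above 0.99. The point does not depend on them.

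**3. Size of the reverse signal for delirium**

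Inputs: 74 with and 74 without delirium, two-sided 0.05 (protocol). Assumed: the pre-operative marker is unrelated to delirium, and delirium later shifts the marker by δ SD. The approximate rejection rate is Φ(δ·√(74/2) − 1.96) = Φ(6.08δ − 1.96).

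| δ (SD) | Formula | Simulation (2,000 runs) | Pre-operative marker, simulated |
|---|---|---|---|
| 0.2 | 0.23 | 0.22 | 0.05 |
| 0.3 | 0.45 | 0.45 | 0.04 |
| 0.4 | 0.68 | 0.68 | 0.05 |
| 0.5 | 0.86 | 0.87 | 0.05 |

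A two-sample t-test stood in for the log-link model.

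**4. Decline (secondary)**

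If the long-term phase starts at 2 months, as in the piecewise model of B.2.3 Project 1 Aim 1, and runs to 8 years, the share before sampling is (48 − 2)/(96 − 2) = 46/94 = 49%.

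For a simulation with N = 148 and 34% positive (B.1.3, H2b), slope SD is 1.3/3/0.48 = 0.90 points per year (Table 3 effect and the d = 0.48 in B.1.3). Assumed: residual SD 2 to 3 points; GCP at 2, 6, 12, 18, 24, 30 and 36 months and 5 and 8 years, or annual late visits. Positivity marks only decline in years 0–4 and has no effect of its own on later decline.

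| Test | Early and late slopes uncorrelated | Correlation 0.5 |
|---|---|---|
| Whole 8-year slope | 42–50% (d = 0.5); 79–89% (d = 0.8) | – |
| Post-sampling slope, unadjusted | about 5% | 12–47% |
| Post-sampling slope, adjusted for observed earlier slope | – | 6–27% |

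A second set-up (annual visits, slope SD 0.5, residual SD 1, marker correlated 0.2 to 0.4 with early slope) gives 24–72% for the whole slope and about 5% after sampling. With slope correlation 0.5 these become 35–89% and 13–37%.

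**5. Precision of the post-sampling test**

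The plan's d = 0.53 for H2b reproduces. With 128 patients and 34% positive, (1.96 + 0.84)·√(1/43.5 + 1/84.5) = 0.52, and Lehr's rule with the harmonic mean gives 0.53.

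If only the 5- and 8-year waves follow sampling, the sum of squared time deviations is 2 × 1.5² = 4.5, against 49.5 for the assumed full schedule. Take a constant slope per person.

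- Residual SD 2: √(0.81 + 4/4.5) = 1.30 against √(0.81 + 4/49.5) = 0.94, ratio 1.4.
- Residual SD 3: √(0.81 + 9/4.5) = 1.68 against √(0.81 + 9/49.5) = 1.00, ratio 1.7.

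Annual visits give 1.2 to 1.4. On the scale of the full-window slope, 0.53 becomes roughly 0.73 to 0.89 with two late waves.

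**The case against.** - **The programme's vulnerability question is answered elsewhere.** Project 1 Aim 1 (SAGES II CSF before anesthesia), Project 1 Aim 3 (stored pre-operative plasma), Project 2 H1C (SAGES II plasma and CSF) and the PREOP plasma in Project 2 Aim 3 are all correctly ordered. This stands: a reader might infer that the whole programme confuses cause and consequence, and the documents do not support that. What lacks a stated, correctly ordered counterpart is the joint inflammatory-plus-AD CSF model.
- **Reversing the regression tests nearly the same association.** True for the unadjusted p-value. But the estimand, the adjustment for time since surgery and the conclusion that may be drawn all change, and the protocol states the conclusion it expects.
- **Project 1 H2b is not the same fault.** This also stands. H2b never has delirium as an outcome, Aim 2 is worded as associations, and the hypothesis statement and 8-year time basis are not printed; the piecewise model shown for Aim 1 ends at 36 months. The documents do not support reading H2b as predicting delirium backwards in time.
- **The simulated rates build in a real association and then find it.** Correct. They show how readily a consequence would appear as a predictor; they are not type I error rates.

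**Conclusion.** The stated analysis for Project 2 Aim 3 is wrong as written for LTFU CSF and LTFU plasma against index delirium, and nothing else in the protocol repairs it. This follows from the dates alone. The 22% to 87% depends on an assumed shift of 0.2 to 0.5 SD.

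For decline, in Project 1 H2b and the LTCD part of Project 2 Aim 3, the point is secondary. About half of an 8-year window precedes sampling, so a slope over the whole window mixes antecedent and subsequent decline. The 8 years for Project 2 is taken from Table 4, and sampling at 4 years is approximate. A reader might infer that restricting the test to decline after sampling cures this. It does so only if early and late slopes are uncorrelated. At a correlation of 0.5 some reverse association remains even after adjustment, because early decline is measured with error. All the decline rates rest on an assumed visit schedule, residual SD and slope correlation. The protocol does not print the SAGES I schedule for the first 36 months, and for later years it gives waves at 5 and 8 years in Table 4 but annual testing in A.3.

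**What to change.** **Project 2 Aim 3 (B.1.3 and B.2.3)**

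1. Limit incident-delirium models in SELECT to PREOP plasma, and label POD2 plasma as concurrent.
2. For LTFU plasma and CSF, make the marker the outcome and index delirium the exposure, adjusted for time since surgery, in line with Project 5 Aim 3.
3. Replace the expected effects on delirium with association with prior delirium.
4. Test the joint inflammatory-plus-AD CSF model for delirium (H3B) in SAGES II.

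**Decline (Project 1 H2b, Project 2 Aim 3 LTCD)**

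5. Report the biomarker's association with pre-sampling and with post-sampling decline separately. Adjust the post-sampling analysis for pre-sampling decline, and claim prediction only from it.
6. State that this adjustment reduces but does not fully remove reverse association, and that d = 0.53 does not apply to the post-sampling test.

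**Cost.** In SELECT, only analysis wording changes. H2b loses precision materially, by about 1.4 to 1.7 fold if only two waves follow sampling. For item 4, only SAGES II patients with CSF contribute, and the protocol does not say whether the inflammatory markers named in H3B are among the proteins to be measured there, so this must be confirmed.

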B. Statistical Considerations

B.1. Sample Size Justification:

Our sample sizes were chosen based on an iterative process involving determining the size of the target population eligible, feasibility constraints, and then verifying adequate power to test the hypotheses across all of our proposed studies for Projects 1-5. Through these detailed considerations, and input from our expert statisticians, we have been able to verify adequate power to address all of our study aims with the proposed sample sizes for the SAGES I SELECT subsample (N=148), the SAGES II cohort (N=460) and the SAGES II subsample (N=180). Power has similarly been verified for all aims of each project. For SAGES II, approximately 50% of the cohort will be enrolled at BIDMC and 50% at BWH. The data, however, will be analyzed together. Computations allow for two-sided type-I error probability 0.05 and to take into account cumulative attrition consistent with our experience in this population. We use multiple imputation to account for missing data where appropriate.

B.1.2. Experimental design and sampling: general considerations

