This study uses observational, prospectively collected cohort data for SAGES I and II. In specific cases, participants experiencing delirium during the index hospitalization will be matched to those without delirium on the basis of age and other factors. To obtain the probability sample of 148 existing SAGES I participants, a matched sampling procedure was piloted. This approach selects all SAGES I participants who had delirium during their index hospitalization and a sample of the non-delirious frequency-matched to the delirious on general cognitive performance (GCP) and age, both key predictors of long term cognitive decline (LTCD). We anticipate enrolling 74 participants with delirium during index hospitalization, and a corresponding 74 participants without. The nondelirious set will be chosen to have a similar distribution to those with delirium on a propensity score derived from a predictive model for delirium, taking into account SAGES I baseline GCP, age, and their interaction. To demonstrate the feasibility and validity of this approach, we conducted a pilot study that constructed 1001 such matched samples, and estimated the standardized mean difference (delirious minus nondelirious) on GCP, age and Charlson comorbidity index for each. While delirious patients in SAGES I were older, had lower GCP, and greater comorbidity than the nondelirious, the frequency matching effectively eliminated these imbalances. Pre-operative standardized mean difference in GCP score was -0.58; after matched selection, the difference decreased to -0.06 (95% CI: -0.13 to 0.011). For age, the pre-operative difference decreased from 0.29 to -0.04 (-0.16, 0.09) after matching. Likewise for the Charlson, the difference was reduced from 0.18 to 0.09 (-0.05, 0.26). These pilot data demonstrate the feasibility and effectiveness of this approach in reducing potential confounding bias, even for unmatched variables. Of

note, we originally powered analyses for a SAGES I probability sample size of 128 (64 per group) and SAGES II sample size of 400. Because we have expanded the sample sizes (to 148 and 460, respectively) and because power increases with sample size, we expect to exceed the estimated power described in the following sections.

B.1.3. Power by Project:

Project 1

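### Project 2 H3B picks the best of four inflammatory markers and the best of four AD biomarkers, then reads the two winners as significant effects in the same patients, so each winner's false-positive rate is about 9–19% instead of 5%

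*Protocol*

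**What the plan says.** Protocol section B.2.3, Project 2, Aim 3 Analysis, describes two steps.

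- **H3A** relates inflammatory proteins and the inflammatory index to delirium and long-term cognitive decline (LTCD): "We will examine plasma markers at PREOP, POD2, and LTFU, and CSF at one time point, LTFU".
- **H3B** follows: "we will select the most predictive inflammatory (IL-6, CRP, sTNFR1, or the inflammatory index) and AD biomarker". The AD candidates are Aβ42, t-tau, p-tau and the p-tau/Aβ42 ratio. Both winners go into one generalized linear model. The stated expectation is: "We expect significant independent effects of both inflammatory markers and CSF AD biomarkers on delirium and LTCD".

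Section B.1.3 (Project 2, Aim 3) places the analysis in the 148 SAGES I SELECT patients, 74 with and 74 without delirium, and sets the level: "We use a relative risk of 1.5 as the threshold of clinical significance, and a type-I error of 0.05". Section B.1 adds that tests are two-sided: "Computations allow for two-sided type-I error probability 0.05".

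Neither place mentions a separate selection sample, a hold-out, resampling or an adjustment for the choice among candidates.

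**The concern.** A marker chosen because it has the strongest association with an outcome, then tested against that outcome in the same patients, does not have the nominal error rate. Its p-value is in effect the smallest of four, and its coefficient is the largest of four, so significance is too easy and the effect size is overstated.

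H3B is where Project 2 asks whether inflammation and AD pathology each contribute to delirium and decline. An inflated rate would credit a whole marker class with an independent effect when none of its members is related to the outcome.

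The protocol guards against this problem elsewhere. Project 2 Aims 1 and 2 validate in an independent sample. Project 4 sets aside a 33% test sample, uses bootstrap replication, and criticises stepwise selection as overly optimistic. Project 5 uses 10-fold cross-validation and ridge regression. Project 2 Aim 3 has no such safeguard.

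**Working it through.** **The plan's own figure.** The protocol states no false-positive rate for H3B. The nearest figure is the Aim 3 power: "a type-I error of 0.05, and calculate 0.84 power for delirium and 0.80 for LTCD", for a relative risk of 1.5. The reference proportion is not given, so this can be neither confirmed nor refuted.

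- Marker positivity of 0.50 v 0.75 (ratio 1.5), two-sided 0.05, gives 0.84 with 64 per group, the sample size first used for power according to section B.1.2. It gives 0.89 with 74 per group.
- Reference proportions from 0.2 to 0.6 give 0.29 to 0.99 with 74 per group.

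The point below does not depend on this figure.

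**Inputs for the error rate**
- Candidates: 4 inflammatory and 4 AD markers, one winner from each (B.2.3).
- Level: two-sided 0.05 (B.1, B.1.3). Sample: 148, 74 v 74 (B.1.3).
- Assumption: most predictive means the largest absolute association with the outcome.
- Assumption: correlation r among candidates from 0 to 0.8. The protocol gives none.

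**Formula for independent candidates.** P(best of 4 significant) = 1 − 0.95⁴ = 1 − 0.8145 = 18.5%. Correlation lowers this.

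**Simulation under no effect.** Normal markers unrelated to the outcome; n = 148; outcome either continuous or split 74/74. In each class the marker with the largest absolute correlation with the outcome is taken. Both winners are fitted in one linear model, and each is tested at two-sided 0.05. Two structures were used: four separate, equally correlated markers; and shared components, where the index is built from two listed inflammatory markers (an assumption) and the ratio from p-tau and Aβ42. With no selection, the same model gives 4.7%.

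| r | Each winner, separate | Each winner, shared | At least one, separate | At least one, shared |
|---|---|---|---|---|
| 0 | 18% | 15–16% | 33% | 28% |
| 0.3 | 17–18% | 14–15% | 30–31% | 27% |
| 0.5 | 15–16% | 12–13% | 28–29% | 23–24% |
| 0.7 | 12–14% | 11–13% | 24% | 22–23% |
| 0.8 | 11–12% | 9–12% | 21–22% | 20–22% |

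The range for each winner is therefore about 9% (shared components, r = 0.8) to 18.5%, or 9–19% after rounding.

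For at least one winner, the upper end is 1 − 0.95⁸ = 33.7%. If both classes sat near the bottom, at 9.5%, the rate would be 1 − 0.905² = 18.1%. That gives about 18–34%.

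Both winners are falsely significant together in only about 1–4%.

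**After a fix.** One pre-specified pair: 4.7% per marker. Bonferroni over four candidates: 0.05/4 = 0.0125 each, so 1 − 0.9875⁴ = 4.9% per class if independent.

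**The case against.** **The premises are partly inferred.** The Aim 3 analysis text gives no metric for most predictive and no alpha for H3B; the 0.05 comes from the power section. This stands as a qualification. Association with the outcome is still the natural reading, and that power section covers the same aim, patients and both marker types.

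**The detail may sit elsewhere.** Section B.2.2 refers to fuller analytic descriptions in the project proposals, and a statistical analysis plan may exist. Silence on an adjustment alone would not be a finding. Here, however, the protocol itself fixes a select-then-test rule, which another document would have to override.

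**H3B is introduced as a study of interactions.** Selecting on marginal association leaves a later interaction test near its nominal level (4–5% in simulation). But the model described names no interaction term, and the stated expectation is about independent effects. Those coefficients carry the inflated error.

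**Stronger readings that the protocol does not support**
- A reader might take 15% as a floor. It is not: strong correlation, or an index and ratio that share components with other candidates, brings the rate to about 9–13%.
- A reader might multiply four markers by the three plasma times and one CSF sample to get 16 candidates. If H3B did select over all of these, the inflammatory rate would be higher. But those specimens and times are listed for H3A, and the text does not say that H3B selects across them.
- A reader might conclude that the joint claim, effects of both classes, is often false. With no effect in either class it arises in only about 1–4%. It would be more frequent if one class had a real effect.

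**Importance.** H3B is one sub-hypothesis of one aim in an observational programme, and it drives no treatment or safety decision. That limits the severity. It does not make the analysis exploratory: Table 1 gives that label to Project 1 Aim 3 but not to Project 2 Aim 3, which has its own power statement.

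**Conclusion.** The concern holds as a should-fix point. H3B chooses winners and tests them in the same patients, with a type-I error of 0.05 stated for the aim and nothing to account for the choice. Each winner's false-positive rate is then about 9–19%, roughly two to four times nominal, and at least one of the two is falsely significant in about 18–34%. Estimates for the winners are biased upward.

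These figures are per outcome and rest on three assumptions: selection by association with the outcome, candidate correlations of 0 to 0.8, and the 0.05 level being applied to H3B. Because section A.2 offers PET to participants who cannot have a lumbar puncture, fewer than 148 may have CSF. That barely changes the error rate.

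**What to change.** **Preferred.** Replace the selection rule by naming one inflammatory marker, with its specimen and time point, and one AD biomarker in advance, and test those two at two-sided 0.05. The choice is the sponsor's. CRP and the inflammatory index both appear in the Aim 3 title, so either is a natural inflammatory choice. The protocol gives no AD biomarker the same priority, so that one needs a stated reason. Report the other markers as exploratory.

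**If selection is kept.** State the metric and the full candidate list, including specimen and time point. Take p-values from a max-statistic permutation test that repeats the selection in every permutation, or use Bonferroni at 0.0125 for each of the four candidates in a class. Bootstrap the whole procedure, selection included, for the intervals.

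**Cost.** A few sentences of protocol or analysis-plan text and a few minutes of computing. Keeping the selection means a stricter threshold and therefore some loss of power. Naming the pair in advance keeps the 0.05 threshold but gives up the chance to choose the marker after seeing the data.
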